### 4.2 Study Design

This is a single-arm, non-randomized pilot study to evaluate the efficacy and tolerability of combination of **two standard of care interventions** (quad-shot palliative radiotherapy and pembrolizumab immunotherapy) for patients with advanced/recurrent/metastatic head and neck cancer.

Fifteen patients will be enrolled who have no curative localized treatment options, are eligible for palliative immunotherapy (pembrolizumab), have a lesion that can be targeted by radiotherapy, and are eligible for palliative radiotherapy as recommended by their radiation oncologist.

Quad-Shot Radiotherapy in Combination with Immune Checkpoint Inhibition for  
Advanced/Recurrent Head and Neck Cancer  
Wake Forest Baptist Comprehensive Cancer Center  
WFBCCC60320

Patients eligible for this study will be those scheduled to receive palliative immunotherapy with the immune checkpoint inhibitor pembrolizumab (which is standard of care) for advanced, R/M head and neck SCC according to standard of care practice. They will also be eligible for palliative quad-shot radiotherapy according to the standard of care for advanced/recurrent/metastatic HSNCC. Quad-shot radiotherapy will be applied between immunotherapy cycle 2-3 or between immunotherapy cycle 3-4, within the last week of the cycle, and not to be delivered on the same day as ICI administration. Up to two additional quad-shot cycles will be delivered between cycles 6-7 or 7-8 (prior to cycle 8) and 11-12 or 12-13 (prior to cycle 13) of immunotherapy. The additional quad-shot treatments will be delivered in a similar fashion, in the last week of the ICI cycle.

Restaging imaging with CT, MRI or PET/CT will be obtained every 5-6 immunotherapy treatments. For the purposes of lesion measurements, follow-up imaging must be performed using the same modality (CT or MRI) as was used for initial baseline imaging. PET/CT may be utilized for follow-up imaging at the clinician's discretion. The maximum response in the targeted lesion and in the non-targeted lesions will be assessed. Subsequent immunotherapy cycles will be delivered after quad-shot radiotherapy until tumor progression or treatment intolerance.

Palliative local (non-systemic) interventions to other sites that are not quad-shot radiotherapy target sites is allowable while on study protocol treatment for the management of cancer symptoms. This should not be utilized for progression of disease at that site.

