## 4.3 Radiotherapy

4.3.1 Patient Positioning and Simulation: Patients will be simulated using CT simulation with or without contrast at the discretion of the treating physician. Immobilization will be employed at the discretion of the treating radiation oncologist.

4.3.2 Target Delineation:

- Gross Tumor Volume (GTV): the target lesion will be identified and delineated as GTV.
- Clinical Target Volume (CTV): areas at risk of subclinical disease around the GTV may be delineated at the discretion of the treating radiation oncologist.
- Planning Target Volume (PTV): 0.3-1 cm isotropic expansion from the GTV or CTV (if present).
- Diagnostic imaging including but not limited to CT, MR, and PET/CT imaging may be utilized to guide target delineation

4.3.3 Radiotherapy Planning:

- Each cycle of quad-shot radiotherapy will be comprised of 14.8 Gy in 4 fractions (3.7 Gy per fraction) delivered twice daily (at least 6 hours apart) over two consecutive days.
- All patients will receive 1 cycle of quad-shot radiotherapy between ICI cycles 2-3.
- Subsequent cycles may occur between immunotherapy cycles 6-7 and 11-12, if more than 1 cycle can be safely delivered at the discretion of the treating radiation oncologist. The eligibility for subsequent cycles will be at the discretion of the treating radiation oncologist.

Therefore, the total prescription dose will be:

- o 14.8 Gy in 4 fractions for those that complete 1 cycle (all patients will receive 1 cycle)
- o 29.6 Gy in 8 fractions for those that complete 2 cycles
- o 44.4 Gy in 12 fractions for those that complete 3 cycles

- Upon planning the initial cycle of quad-shot radiotherapy, a composite plan will be generated to assess the total dose to the target/organs at risk (see below).
  - o If deemed appropriate by the treating radiation oncologist, the same plan may be delivered for up to 3 cycles.
  - o If deemed appropriate by the treating radiation oncologist, re-simulation may be performed in order to plan subsequent cycles. This may be necessary to account for anatomic changes that may have occurred in the interim (between quad-shot cycles) which would otherwise impact dose to the target or organs at risk.

4.3.4 Organs at Risk (OAR): Organs at risk will vary depending on the location of the target lesion and will be delineated at the discretion of the treating radiation oncologist. No target or normal tissue constraints are mandated by this protocol. However, optional clinical goals are below:

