### **5.0 Study Outcomes and Study Measures**

#### **5.1 Primary Outcome**

- 5.1.1 The overall response rate will be measured according to RECIST 1.1 (Section 7.1.3).

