### **6.5 Duration of Follow Up**

Patients will be followed for a minimum of 2 times every 30 days after the last study drug is administered for adverse events monitoring. Follow-up for serious adverse events and mortality after the last study dose is administered will take place during the routine clinic visits that the patient will have during the 60-day follow-up window (Also referenced in Appendix D). If no visit occurs during this window, a phone call confirmation should be made to the patient to determine vital status and whether any adverse events and in particular, Grade 4 unexpected adverse events occurred during that window of time and recorded on Appendix F.

Patients will be followed according to the treating physician after removal from study or until death, whichever occurs first. Patients removed from study for unacceptable adverse events will be followed until resolution or stabilization of the adverse event.

Patients will be followed until death for monitoring survival study endpoints. Frequency of visits will be established by the treating physician and will be done in person or over the phone. Tumor imaging will be also performed at the discretion of the treating physician and results will be collected from the medical records. Alternatively, if the patient stops visiting with our clinic, tumor status and survival information will be collected by phone from the patient and from any other oncology office.

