### **6.6 Criteria for Removal from Study**

Patients will be removed from study when any of the following criteria apply:

Quad-Shot Radiotherapy in Combination with Immune Checkpoint Inhibition for Advanced/Recurrent Head and Neck Cancer  
Wake Forest Baptist Comprehensive Cancer Center  
WFBCCC60320

- Patient withdrawal of consent or loss to follow-up.
- Adverse event that, in the opinion of the investigator or the sponsor, contraindicates further dosing.
- Subject is determined to have met one or more of the exclusion criteria for study participation at study entry and continuing investigational therapy might constitute a safety risk.
- Pregnancy or intent to become pregnant
- Grade  $\geq 3$  infusion reaction.
- Subject noncompliance that, in the opinion of the investigator or sponsor, warrants withdrawal; eg, refusal to adhere to scheduled visits.
- Initiation of alternative anticancer therapy including another investigational agent.
- Confirmation of PD and investigator determination that the subject is no longer benefiting from protocol treatment.
- Death.

Subjects who are permanently discontinued from further receipt of investigational product, regardless of the reason (withdrawal of consent, due to an AE, other), will be identified as having permanently discontinued treatment.

Subjects who are removed from study prior to completing at least 2 cycles of ICI followed by at least 1 cycle of quad-shot radiotherapy followed by at least 2 cycles of ICI will be discontinued from the study and replaced.

Subjects who are permanently discontinued from receiving investigational product will be followed for safety until follow-up criteria are met in Section 6.4. Subjects who decline to return to the site for evaluations will be offered follow-up by phone for at least 60 days as an alternative.

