### 7.1.3 Response Criteria

- **Definition of complete response (CR)** for target and non-target lesions, as appropriate
  - Target Lesions:
    - Disappearance (or decrease to the point at which measurement is not possible) of all target lesions. **Any pathological lymph nodes (whether target or non-target) must have reduction in short axis to <10 mm** (the sum may not be “0” if there are target nodes)
  - Non-target lesions:
    - Disappearance (or decrease to the point at which measurement is not possible) of all non-target lesions. **All lymph nodes must be non-pathological in size (< 10 mm short axis)**
- **Definition of partial response (PR)** for target and non-target lesions, as appropriate
  - Target lesions:
    - At least a 30% decrease in the sum of diameters of target lesions, taking as reference the baseline sum of diameters
  - Non-target lesions
    - **Non-CR/Non-PD:** Persistence of 1 or more **non-target lesion(s)**.
- **Definition of progressive disease (PD)** for target and non-target lesions, as appropriate
  - Target Lesions:
    - > 20% increase in the sum of the longest diameters (SLD) taking as reference the smallest SLD recorded since the treatment started (nadir) **and minimum 5 mm increase over the nadir**
    - When sum becomes very small, increases within measurement error (2-3 mm) can lead to 20% increase
    - (Note: the appearance of one or more new lesions is also considered progressions)
  - Non-target lesions:
    - *Unequivocal progression* of existing non-target lesions. The appearance of one or more new lesions.
    - *Unequivocal progression* should not normally trump target lesion status. It must be representative of overall disease status change, not a single lesion increase
    - Although a clear progression of “non-target” lesions only is exceptional, the opinion of the treating physician should prevail in such circumstances, and the progression status should be confirmed at a later time by the review panel (or Principal Investigator).

- **Definition of stable disease (SD)** for target and non-target lesions, as appropriate
  - Target lesions:
    - Neither sufficient shrinkage to qualify for PR nor sufficient increase to qualify for PD, taking as reference the smallest sum diameters while on study
- **Definition and evaluation of best overall response**, if applicable  
The best overall response is the best response recorded from the start of the treatment across all time points.

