#### 7.1.4 Duration of Response

Duration of overall response: The duration of overall response is measured from the time measurement criteria are met for CR or PR (whichever is first recorded) until the first date that recurrent or progressive disease is objectively documented by clinical, radiographic, or pathologic findings (taking as reference for progressive disease the smallest measurements recorded since the treatment started).

The duration of overall CR is measured from the time measurement criteria are first met for CR until the first date that progressive disease is objectively documented.

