## 11.0 Statistical Considerations

### 11.1 Analysis of Primary Objective

11.1.1 For this pilot study, the primary analytic objective is to measure the overall response rate measured according to RECIST criteria and determine the percent of patients with either a partial or complete response (PR or CR) and the corresponding 95% Clopper Pearson exact confidence interval. This estimate will provide useful information concerning the potential efficacy of this treatment for planning future studies.

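### Best overall response has no stop at progression or at new anticancer therapy, so a patient with documented PD and a later PR or CR could count as a responder in the primary ORR

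*Combined protocol and SAP*

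**What the plan says.** **Endpoint.** Section 7.1.3 states: "The best overall response is the best response recorded from the start of the treatment across all time points". Section 5.1.1 refers the primary outcome to 7.1.3, and 11.1 counts every patient with PR or CR. Section 4.2 adds only this: "The maximum response in the targeted lesion and in the non-targeted lesions will be assessed". The table in 7.1.3 combines target, non-target and new-lesion status into an overall response. It has no rule that an earlier PD bars a later PR or CR.

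**Related endpoints.** Progression is a PFS event (7.1.5). Duration of response runs from first CR or PR "until the first date that recurrent or progressive disease is objectively documented" (7.1.4).

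**Treatment after PD.** Sections 4.2 and 4.4.2 give pembrolizumab until progression. Section 6.4 ends therapy for progression only when local therapy cannot deal with it. Section 6.6 lists as a ground for removal: "Confirmation of PD and investigator determination that the subject is no longer benefiting from protocol treatment". Section 4.5 allows local treatment of limited progressing disease outside the quad-shot region, whereas 4.2 says palliative local treatment should not be used for progression at that site. On quad-shots 2 and 3, Section 4.3.3 says: "The eligibility for subsequent cycles will be at the discretion of the treating radiation oncologist".

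**Imaging after treatment.** Section 6.5 says: "Tumor imaging will be also performed at the discretion of the treating physician and results will be collected from the medical records".

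**The concern.** A best response taken over an open-ended window can only stay the same or improve as scans are added. If scans after PD enter it, a patient who has already failed by the protocol's own criteria can be turned into a responder, possibly by later treatment rather than by the combination under study.

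The ORR is the pilot's main result, and 11.3 says it will be used to judge whether further study is warranted. A patient counted as a responder after PD would also be a PFS event. The duration of that response would either have no valid value, because the first PD date precedes the response, or begin after documented failure. The plan does not say which.

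**Working it through.** **1. The plan's own figure.** Section 11.3 gives a maximum exact 95% interval width of 0.52 with 15 evaluable patients, at 7/15. The Clopper-Pearson limits for 7/15 are 0.2127 and 0.7341, a width of 0.5215. The figure is reproduced, and it does not depend on the response window.

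**2. Can PD followed by PR occur under the stated criteria?** Take illustrative target sums of 50 mm at baseline, 61 mm at the scan after cycle 5, and 34 mm later.
- 61/50 = 1.22, so +22% and +11 mm. This meets PD (more than 20% and at least 5 mm over the nadir).
- 34/50 = 0.68, so -32% from baseline. This meets PR (at least a 30% decrease from baseline).

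Under 7.1.3 the best overall response is PR. Under 7.1.5 the patient had a PFS event at the first scan.

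**3. Is the timing possible?** Section 7.1 puts the first response evaluation after 5 cycles and the next after 10 if pembrolizumab continues. Quad-shot 2 falls between cycles 6-7 or 7-8 (4.3.6), so a PD at the first scan would precede it. The irradiated lesions are the target lesions (7.1.1). Three routes are not closed by the text:
- target PD, pembrolizumab continued under 6.4 or 6.6, then shrinkage at a later scan;
- PD from a new lesion that is treated locally (4.5), with a later assessment recorded as having no new lesion. A new lesion that persists keeps the assessment at PD;
- a scan collected under 6.5 after treatment has ended, possibly after other therapy.

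**4. Size per patient.** 1/15 = 6.7 points. Exact 95% intervals:

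| Responders | ORR | 95% CI |
|---|---|---|
| 3/15 | 20.0% | 4.3 to 48.1% |
| 4/15 | 26.7% | 7.8 to 55.1% |
| 5/15 | 33.3% | 11.8 to 61.6% |
| 6/15 | 40.0% | 16.3 to 67.7% |

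The top of the benchmark in 11.3 is 36%, and 0.36 × 15 = 5.4, so 6/15 is the first count above it.

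**5. Sensitivity.** Let p be the response rate before progression and q the share of the remaining patients who progress first and respond later. The counted rate is p + (1 - p)q. The documents give no value for q; 5%, 10% and 20% are assumptions. The table shows the counted rate, then the binomial probability of at least 6/15.

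| p | q = 0 | q = 5% | q = 10% | q = 20% |
|---|---|---|---|---|
| 13% | 13%; 0.8% | 17.4%; 3.3% | 21.7%; 8.6% | 30.4%; 29.0% |
| 17% | 17%; 3.0% | 21.2%; 7.7% | 25.3%; 15.5% | 33.6%; 39.0% |
| 36% | 36%; 46.8% | 39.2%; 57.2% | 42.4%; 66.9% | 48.8%; 82.6% |

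At p = 17%, the expected number of extra responders is 15 × 0.83 × q, which is 0.6, 1.2 and 2.5.

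**The case against.** A reader might infer that treatment, further quad-shots and imaging all continue past progression, so that responses to salvage therapy will enter the ORR. The documents do not support that.
- Sections 4.2 and 4.4.2 stop pembrolizumab at progression. Sections 6.4 and 6.6 permit more only conditionally, and 6.6 concerns removal from study rather than dosing.
- Quad-shots after PD are neither provided for nor barred. They are placed between pembrolizumab cycles, so they have no slot if pembrolizumab has stopped.
- The imaging sentence in 6.5 belongs to a paragraph on survival follow-up, and alternative anticancer therapy is a ground for removal (6.6). No text says that scans after removal feed best overall response.
- Section 7.1.6 has response assessed during the study, and 11.5 expects response follow-up to end about 3 months after accrual.

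These points limit how often the problem could arise, but they do not close the window. Section 11.5 is an estimate of study length, and patients enrolled early could have many more scans than those enrolled late. Section 7.1.6 sets no cut-off, and independent review is optional. The conflict over treatment after PD means that the answer depends on which section is followed.

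It is also fair to say that this is a pilot without a hypothesis test, that the benchmark is a loose range and that the intervals overlap heavily. A PFS event and a response in one patient are results on two different endpoints, and 7.1.4 is most naturally read as progression after the response. That reading avoids a negative duration, but it makes the duration start after documented failure.

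**Conclusion.** The point stands as a gap in the definition of the primary endpoint. The rule as written counts a PR or CR recorded after documented PD or after new anticancer therapy, and no other section overrides it. Any resulting bias in the ORR is upward, at 6.7 points per patient of 15. One patient is enough to carry 5/15 past the top of the plan's benchmark.

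The number affected cannot be derived from the documents and may be zero; the sensitivity figures rest on assumed values of q. The conclusion requires only that PD followed by response is possible and unaddressed. It does not require that treatment routinely continues after PD. Because this defines the primary endpoint, it should be settled before responses are tabulated.

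**What to change.** In 7.1.3:
- **Primary ORR.** Define best overall response as the best response from the start of treatment up to the first documented overall PD or the last assessment before new systemic anticancer therapy, whichever is first.
- **Target-lesion response (5.2.1).** Use a separate window that ends at target-lesion PD or new systemic anticancer therapy. Target-lesion PD here should rest on the sum of diameters alone, because the note under target lesions in 7.1.3 also counts new lesions as progression. A distant new lesion should not end the local-response window.
- **Local treatment.** State how assessments after non-protocol local treatment of a lesion are handled.
- **Later responses.** Report responses after the cut-off separately and descriptively, outside the ORR.

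The sponsor must also reconcile the passages on treatment past progression (4.2, 4.4.2, 4.5, 6.4, 6.6). No clinical rule is proposed here.

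**Cost.** A few sentences in 7.1.3 and a descriptive line in the report, with no added data. The 15 evaluable patients and the 0.52 maximum width are unchanged. The downside is that the ORR may be slightly lower, and delayed responses after apparent progression appear outside it.

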#### Criteria for Determination of Best Overall Response

Target Lesion	Non-Target Lesion	New Lesions	Overall Response
CR	CR	No	CR
CR	Non-CR/Non-PD	No	PR
CR	NE	No	PR
PR	Non-PD or not all evaluated	No	PR
SD	Non-PD or not all evaluated	No	SD
Not all evaluated	Non-PD	No	NE
PD	Any	Yes or No	PD
Any	PD	Yes or No	PD
Any	Any	Yes	PD

#### 7.1.4 Duration of Response

Duration of overall response: The duration of overall response is measured from the time measurement criteria are met for CR or PR (whichever is first recorded) until the first date that recurrent or progressive disease is objectively documented by clinical, radiographic, or pathologic findings (taking as reference for progressive disease the smallest measurements recorded since the treatment started).

The duration of overall CR is measured from the time measurement criteria are first met for CR until the first date that progressive disease is objectively documented.

#### 7.1.5 Survival Outcomes

Progression-Free Survival is defined as the duration of time from registration to the time of progression, death, or date of last contact; those lost to follow-up will be censored.

Overall Survival is defined as the duration of time from registration to date of death or date of last contact; those lost to follow-up will be censored.

#### 7.1.6 Response Review

Quad-Shot Radiotherapy in Combination with Immune Checkpoint Inhibition for Advanced/Recurrent Head and Neck Cancer  
Wake Forest Baptist Comprehensive Cancer Center  
WFBCCC60320

Response will be assessed by the principal investigator(s) during the course of the study.

Following study completion, responses may be reviewed by independent expert neuroradiologist(s). Simultaneous review of the patients' files and radiological images is the best approach.

## 8.0 Adverse Events List and Reporting Requirements

The Principal Investigator is responsible for ensuring that all staff involved in the study is familiar with the content of this section.

### 8.1 Safety Parameters

#### **Definition of adverse events:**

The International Conference on Harmonization (ICH) Guideline for Good Clinical Practice (GCP) E6(R1) defines an AE as:

Any untoward medical occurrence in a patient or clinical investigation subject administered a pharmaceutical product and which does not necessarily have a causal relationship with this treatment. An AE can therefore be any unfavorable and unintended sign (including an abnormal laboratory finding), symptom, or disease temporally associated with the use of a medicinal product, whether or not considered related to the medicinal product.

An AE includes but is not limited to any clinically significant worsening of a subject's pre-existing condition. An abnormal laboratory finding (including ECG finding) that requires an action or intervention by the investigator, or a finding judged by the investigator to represent a change beyond the range of normal physiologic fluctuation, should be reported as an AE.

Adverse events may be treatment emergent (ie, occurring after initial receipt of investigational product) or nontreatment emergent. A nontreatment-emergent AE is any new sign or symptom, disease, or other untoward medical event that begins after written informed consent has been obtained but before the subject has received investigational product.

Elective treatment or surgery or preplanned treatment or surgery (that was scheduled prior to the subject being enrolled into the study) for a documented pre-existing condition, that did not worsen from baseline, is not considered an AE (serious or nonserious). An untoward medical event occurring during the prescheduled elective procedure or routinely scheduled treatment should be recorded as an AE or SAE.

The term AE is used to include both serious and non-serious AEs.

